7.8. Impact of the COVID-19 Pandemic

Targeted summaries and listings will be presented to assess the impact of the COVID-19 pandemic on study disruptions, including alternative methods of assessment, missed visits, and collection of central laboratory data for efficacy endpoints. Assessment of protocol deviations due to COVID-19 is described in [Section 7.3](#).

The following will be summarized by treatment group and overall at the interim analysis and final analysis:

- Patient count of missed visits by visit (overall and due to COVID-19)
- Patient count of visit type (onsite, phone, video, home health care, medical record review, other) by visit
- Patient count of missed central laboratory eGFR and UP/C assessments by visit (overall and due to COVID-19)
- Patient count of missed edema assessments by visit (overall and due to COVID-19)
- Patient count of missed blood pressure assessments by visit (overall and due to COVID-19)
- Patient count of local laboratory collection (eGFR only, UP/C only, any local labs) by visit

By-patient listings will be presented for patients discontinuing treatment due to COVID-19 and patients discontinuing the study due to COVID-19. A by-patient listing of all COVID-19 study disruptions, including protocol deviations, will also be presented. COVID-19 study disruptions will be identified from eCRF pages, central laboratory data, and protocol deviations.

8. EFFICACY

8.1. General Considerations

All efficacy analyses will be based on the FAS or IAS, as described below. The primary, surrogate, and secondary endpoint analyses will also be performed on the PP Analysis Set as supportive analyses. All primary efficacy analyses based on laboratory data will use central lab data only. All efficacy analyses specified below refer to the double-blind period only.

UP/C will be determined using first morning void urine samples and will be calculated as the geometric mean of 3 first morning void urine samples collected within 5 days prior to the visit. If one of the samples is missing, the average of the other 2 samples will be used. As UP/C is a highly right-skewed variable, analyses will be performed on log-transformed data. For ease of interpretation, results will be presented in the original units.

The eGFR for each baseline and post-baseline visit will be determined using the CKD-EPI (Levey 2009) formula for patients ≥ 16 years of age at the time of screening and the Modified Schwartz formula for patients < 16 years of age at the time of screening (Schwartz 2009a; Schwartz 2009b).

For the purposes of efficacy analyses, an assessment is considered “on treatment” if it occurs after the first dose of study medication and no more than 3 days after the date of last dose of randomized treatment.

For all least-squares (LS) means that include strata coefficients, the observed strata proportions will be used instead of assuming equal sizes of strata.

8.2. Statement of the Null and Alternative Hypotheses

The final analysis of the primary endpoint in non-US countries will test the following hypothesis using the FAS:

- H_0 : Slope of eGFR over the blinded treatment period (after adjusting for early hemodynamic effects) is equal between sparsentan and irbesartan
- H_1 : Slope of eGFR over the blinded treatment period (after adjusting for early hemodynamic effects) is different between sparsentan and irbesartan

The final analysis of the primary endpoint in the US will test the following hypothesis using the FAS:

- H_0 : Slope of eGFR over the blinded treatment period is equal between sparsentan and irbesartan
- H_1 : Slope of eGFR over the blinded treatment period is different between sparsentan and irbesartan

The interim analysis of the surrogate endpoint at Week 36 will test the following hypothesis using the IAS:

- H_0 : Proportion of patients achieving FPPE at Week 36 is equal between sparsentan and irbesartan

- H₁: Proportion of patients achieving FPRE at Week 36 is different between sparsentan and irbesartan

The final analysis of secondary efficacy endpoints in non-US countries will test the following hypotheses using the FAS:

- H₀₁: Percent change from Week 6 in eGFR at Week 108 is equal between sparsentan and irbesartan
- H₁₁: Percent change from Week 6 in eGFR at Week 108 is different between sparsentan and irbesartan
- H₀₂: Percent change in eGFR from baseline to 4 weeks post-cessation of randomized treatment at Week 112 is equal between sparsentan and irbesartan
- H₁₂: Percent change in eGFR from baseline to 4 weeks post-cessation of randomized treatment at Week 112 is different between sparsentan and irbesartan
- H₀₃: Slope of eGFR over the blinded treatment period is equal between sparsentan and irbesartan
- H₁₃: Slope of eGFR over the blinded treatment period is different between sparsentan and irbesartan

The final analysis of secondary efficacy endpoints in the US will test the following hypotheses using the FAS:

- H₀₁: Slope of eGFR over the blinded treatment period (after adjusting for early hemodynamic effects) is equal between sparsentan and irbesartan
- H₁₁: Slope of eGFR over the blinded treatment period (after adjusting for early hemodynamic effects) is different between sparsentan and irbesartan
- H₀₂: Change in eGFR from baseline to 4 weeks post-cessation of randomized treatment at Week 112 is equal between sparsentan and irbesartan
- H₁₂: Change in eGFR from baseline to 4 weeks post-cessation of randomized treatment at Week 112 is different between sparsentan and irbesartan

The treatment effect refers to the effect of sparsentan minus irbesartan.

8.3. Examination of Subgroups

At the final analyses, select efficacy endpoints (primary, surrogate, and secondary efficacy endpoints; eGFR change and percent change from baseline; and UP/C percent change from baseline) will be analyzed for patient subgroups using the FAS. The surrogate endpoint, eGFR change and percent change from baseline through Week 60, and UP/C percent change from baseline through Week 60 will also be analyzed for patient subgroups at the interim analysis using the IAS. In addition, select safety analyses (TEAEs) will also be analyzed for patient subgroups using the Safety Analysis Set. Baseline subgroups will be assessed at baseline only if there are a sufficient number of patients in each subgroup (eg, >5 patients per group). Post-baseline subgroups will be assessed at the time of analysis.

Baseline subgroups of interest are as follows:

- Age categories: $<18, \geq 18$
- Age categories at FSGS diagnosis: $<18, \geq 18$
- Sex: Male, Female
- Race: White, Black, Asian, Others
- Baseline BMI (kg/m^2): $<27, \geq 27$
- Randomization strata:
 - Screening eGFR ≥ 30 to <60 mL/min/ 1.73m^2 and non-nephrotic (Screening UP/C ≤ 3.5 g/g for patients ≥ 18 years of age and ≤ 2 g/g for patients <18 years of age)
 - Screening eGFR ≥ 30 to <60 mL/min/ 1.73m^2 and nephrotic (Screening UP/C >3.5 g/g for patients ≥ 18 years of age and >2 g/g for patients <18 years of age)
 - Screening eGFR ≥ 60 mL/min/ 1.73m^2 and non-nephrotic (Screening UP/C ≤ 3.5 g/g for patients ≥ 18 years of age and ≤ 2 g/g for patients <18 years of age)
 - Screening eGFR ≥ 60 mL/min/ 1.73m^2 and nephrotic (Screening UP/C >3.5 g/g for patients ≥ 18 years of age and >2 g/g for patients <18 years of age)
- Baseline eGFR ($\text{mL}/\text{min}/1.73\text{m}^2$):
 - $<60, \geq 60$ to $<120, \geq 120$
 - $<120, \geq 120$
- Baseline UP/C (g/g):
 - Non-nephrotic (≤ 3.5 for patients ≥ 18 years of age and ≤ 2 for patients <18 years of age)
 - Nephrotic (>3.5 for patients ≥ 18 years of age and >2 for patients <18 years of age)
- Prior use of the following RAAS inhibitors: Yes, No
 - ACE inhibitors
 - Angiotensin II receptor blockers (ARB)
 - Aldosterone blockers
 - Aliskiren
 - Any RAAS inhibitors
- Baseline use of the following medications: Yes, No
 - Any immunosuppressive agents
 - Steroids
 - Other immunosuppressive agents including CNIs, MMF, azathioprine, ACTH

- Antihypertensive medications (except RAAS inhibitors) including diuretics
- Diuretics
- Statins and other hypolipidemic drugs
- Years since FSGS diagnosis: ≤ 10 , > 10
- Geographic region: North America, Europe, Asia Pacific, South America
- Baseline cardiovascular history: Yes, No
- History of hypertension: Yes, No
- Known mutation in podocyte proteins: Yes, No
- Post-baseline subgroups of interest as follows: Yes, No
 - Achievement of FPRE at Week 36, Week 60, or Week 108
 - Concomitant use (and no baseline use) of antihypertensive medications (except angiotensin-converting enzyme inhibitors [ACEIs], aldosterone blockers, aliskiren, or ARBs)
 - Concomitant use (and no baseline use) of diuretics
 - Concomitant use (and no baseline use) of immunosuppressive medications

Subgroup characteristics will be summarized by treatment group. For efficacy endpoints analyzed by a statistical model, the overall effect of the prognostic factor will be assessed by including a main effect for prognostic factor and a treatment by prognostic factor interaction term in the model. The treatment by prognostic factor interaction effect will be evaluated at a 0.20 level of significance to assess whether treatment effects vary by levels of prognostic factor. If the p-value for the treatment by prognostic factor interaction effect is < 0.20 , descriptive and inferential statistics will be presented for each subgroup level.

Additional subgroup analyses may be performed (eg, based on genetic testing results, exploratory biomarkers).

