4.3.1.1. Surrogate Endpoint: FPPE

Based on the results at Week 8 of the sparsentan Phase 2 DUET study (RET-D-001) in FSGS patients and projected to Week 36, it is assumed that sparsentan will result in approximately 50% of patients achieving FPPE, and that irbesartan will result in approximately 20% of patients achieving FPPE. Based on these assumptions and using a Pearson chi-square test for 2 proportions and a 2-sided α level of 0.05, 190 patients (approximately 95 per treatment group) will yield at least 90% power to detect a difference in response proportions between sparsentan and irbesartan. The minimum treatment difference that could be declared statistically significant is approximately 13% with approximately 190 patients.

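### SAP 8.3 applies the baseline-subgroup interaction test and per-level inference to post-baseline subgroups that treatment can affect, such as FPRE achievers, so those contrasts are not randomized comparisons

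*SAP*

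**What the plan says.** SAP 8.3 sends "select efficacy endpoints (primary, surrogate, and secondary efficacy endpoints", among others, to subgroup analysis at the final analysis. The surrogate is also analysed by subgroup at the interim.

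The list has a baseline part and a post-baseline part. The post-baseline part comprises "Achievement of FPRE at Week 36, Week 60, or Week 108" and concomitant use, without baseline use, of antihypertensives, diuretics and immunosuppressive medication. On timing, the section says "Post-baseline subgroups will be assessed at the time of analysis".

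One method then covers both parts. The model gains the factor itself and its interaction with treatment. On the test, the section says "The treatment by prognostic factor interaction effect will be evaluated at a 0.20 level of significance". Where that test gives p<0.20, the output expands: "descriptive and inferential statistics will be presented for each subgroup level". Section 8.3 gives the post-baseline factors no exemption, no descriptive label and no separate method.

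**The concern.** The section calls these variables prognostic factors, but elsewhere the SAP treats several of them as outcomes. FPRE at Week 36 is the surrogate endpoint (SAP 3.2.1). Starting or intensifying immunosuppression is an exploratory endpoint compared between arms (SAP 3.2.3 and 8.8.4). Hypotension and fluid retention are safety topics of interest (SAP 10.1.2), so new antihypertensive or diuretic use may also respond to treatment.

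Once patients are grouped by something treatment changes, the arms within a group are no longer comparable. If sparsentan brings half of its patients to FPRE and irbesartan a fifth, the irbesartan achievers are the more highly selected group. A difference in slope between the two sets of achievers mixes treatment with selection.

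Two further problems are specific to FPRE:

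- Week 36 FPRE is both a subgroup and the surrogate endpoint.
- Week 60 and Week 108 status is settled long after the slope begins at Day 1 or Week 6, so the slope is conditioned on the future. Because SAP 6.5.4 admits only on-treatment assessments up to Week 108, an observed Week 108 status also requires about two years on treatment.

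What is at stake is the reading of exploratory output. SAP 4.3.1.2 projects the slope benefit from the FPRE difference, so treatment effects by FPRE status will attract attention.

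**Working it through.** **Inputs from the documents.** FPRE: "it is assumed that sparsentan will result in approximately 50% of patients achieving" it and "irbesartan will result in approximately 20% of patients achieving" it (SAP 4.3.1.1). Responder-minus-non-responder gap in chronic slope 8.4; projected treatment differences 2.52 (chronic) and 2.1 (total); SD of total slope 5.50; about 150 patients per group (SAP 4.3.1.2). Slopes are in mL/min/1.73 m² per year.

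**The plan's own figures.** 0.30 × 8.4 = 2.52, as stated. For total slope, SE = 5.50 × √(2/150) = 0.635, and 2.1/0.635 - 1.96 = 1.35, which gives 91.1% power. The stated figure of at least 90% reproduces.

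**Model (my assumption).** Each patient has a standard normal prognosis score. The best 50% on sparsentan and the best 20% on irbesartan reach FPRE. Treatment has no effect on slope.

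**Imbalance in mean score, from truncated-normal means:**

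| | Sparsentan | Irbesartan | Difference |
|---|---|---|---|
| Achievers | 0.3989/0.5 = 0.798 | 0.2800/0.2 = 1.400 | -0.602 |
| Non-achievers | -0.3989/0.5 = -0.798 | -0.2800/0.8 = -0.350 | -0.448 |

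**Moderate case.** Assume a prognostic slope SD of 3 and a correlation of 0.5 to 0.9 between prognosis and the score that drives response.

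- Achievers: 3 × 0.5 × (-0.602) = -0.9 to 3 × 0.9 × (-0.602) = -1.6.
- Non-achievers: 3 × 0.5 × (-0.448) = -0.7 to 3 × 0.9 × (-0.448) = -1.2.

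**Upper bound.** Let the whole 8.4 gap be prognostic. The score gap between responders and non-responders is 0.798 + 0.798 = 1.596 within sparsentan, 1.400 + 0.350 = 1.750 within irbesartan, and 1.492 pooled over arms.

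| Gap scaled to | Slope per score SD | Achievers | Non-achievers |
|---|---|---|---|
| Irbesartan arm | 8.4/1.750 = 4.80 | -2.9 | -2.15 |
| Sparsentan arm | 8.4/1.596 = 5.26 | -3.2 | -2.4 |
| Pooled | 8.4/1.492 = 5.63 | -3.4 | -2.5 |

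If half the gap is prognostic, these halve: about -1.4 to -1.7 in achievers. If none is, the bias is zero. Matching the planned 2.52 in achievers needs a prognostic share between 2.52/3.39 = 74% and 2.52/2.89 = 87%, depending on the scaling.

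**Effect of the 0.20 condition.** I simulated 10,000 null trials per setting (150 per group, slope SD 5.5), fitting a treatment-by-FPRE linear model to patient slopes.

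| Prognosis-slope correlation | False p<0.05 in at least one FPRE level | Interaction p<0.20 | Both, so displayed |
|---|---|---|---|
| 0 | 9% | 20% | 6% |
| 0.50 | 57% | 21% | 18% |
| 0.63 | 79% | 23% | 22% |
| 0.75 | 94% | 24% | 24% |

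The all-randomized comparison kept its error rate (4.9% to 5.4%). The bias has the same sign and a similar size in both levels, so the interaction test hardly detects it. It limits how often a false result is shown, but does not screen out the biased ones: at a correlation of 0.50, 87% of the trials that passed the 0.20 condition showed a false p<0.05.

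**Surrogate by its own status.** Among patients with FPRE at Week 36, the Week 36 response rate is 100% in both arms; among those without, it is 0% in both. The risk difference is zero by definition. A logit fit to Week 36 alone is completely separated.

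No figure was computed for the medication subgroups.

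**The case against.** The strongest reply is that this is exploratory output outside the testing hierarchy of SAP 8.4, shown per level only when the interaction p-value is below 0.20. That is correct. A reader might infer that within-subgroup p-values will routinely appear, or that the primary result is compromised. Neither follows: the 0.20 condition is met in about 20% to 24% of the null trials tabulated, and the primary test is untouched.

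A reader might also infer that a false difference as large as the planned effect is to be expected. The documents do not support that. They give no prognostic share for the 8.4 gap; SAP 7.7 says the underlying model adjusted for potential prognostic factors, and SAP 4.3.1.2 takes the treatment difference to run through response. On the total-slope scale the implied gap is 2.1/0.30 = 7.0. Attributing all of it to prognosis needs a correlation of 7.0/(1.492 × 5.50) = 0.85, which is extreme. The figures near -3 are an upper bound.

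Nor do the calculations show a bias that would flatter the surrogate. In this model it runs against sparsentan in both levels; another mechanism could reverse it, but none was modelled.

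Finally, not every FPRE subgroup is circular for the surrogate. Only Week 36 is exactly so; Weeks 60 and 108 are later readings of the same measure. The 100%-versus-100% table is also useless rather than misleading.

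What remains is that the stated method, followed as written, tests treatment effects conditional on an outcome of treatment. The 0.20 condition does not cure this, since the interaction test itself conditions on the same variable.

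**Conclusion.** The point holds as a fault in a stated analysis rule, of secondary importance. Interaction tests and treatment contrasts within the post-baseline subgroups of SAP 8.3 are not randomized comparisons.

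The size depends on how far FPRE and slope share prognosis, which the documents do not state. Under the moderate assumption the false difference is below the planned effect throughout; it approaches or exceeds the planned effect only if most of the responder gap is prognostic. All these figures assume the planned 50% and 20% rates, a single normal prognosis score and no treatment effect on slope.

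The surrogate by Week 36 FPRE status carries no information under any assumption. For Week 60 and Week 108, the main objection is that slopes are conditioned on later status. For the medication subgroups the argument is qualitative.

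**What to change.** In SAP 8.3:

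1. Limit the interaction test at 0.20 and the per-level inferential statistics to baseline subgroups.
2. Drop the surrogate endpoint by FPRE status.
3. Present the remaining post-baseline subgroups descriptively, labelled as non-randomized comparisons, with no treatment-effect p-values.
4. If eGFR slope is shown by FPRE status, use a Week 36 landmark with eGFR after Week 36 only. State that the landmark removes conditioning on the future but not the selection between arms.

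The existing sensitivity analyses for changes in immunosuppression (SAP 8.5.2 and 8.7) are separate and need no change. The cost is SAP wording and the loss of some exploratory outputs; sample size and power for the primary endpoint do not change.

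### For model-based efficacy endpoints, the SAP specifies by-level subgroup estimates only when the interaction p-value is below 0.20, which exaggerates the differences shown and leaves consistent factors without specified output

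*SAP*

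**What the plan says.** SAP section 8.3 (Examination of Subgroups) states that the primary, surrogate and secondary efficacy endpoints, the change and percent change from baseline in eGFR, and the percent change in UP/C "will be analyzed for patient subgroups using the FAS" at the final analysis. A shorter list applies at the interim analysis. Baseline factors are examined only where numbers suffice, with more than 5 patients per group given as an example.

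The presentation rule comes at the end of the section and is limited in scope: "For efficacy endpoints analyzed by a statistical model", a factor main effect and a treatment-by-factor term are added to the model. Then: "The treatment by prognostic factor interaction effect will be evaluated at a 0.20 level of significance". By-level results follow only on a condition: "If the p-value for the treatment by prognostic factor interaction effect is" below 0.20, "descriptive and inferential statistics will be presented for each subgroup level". The section does not say what is presented when the p-value is 0.20 or higher.

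Safety is treated differently: "select safety analyses (TEAEs) will also be analyzed for patient subgroups using the Safety Analysis Set", with no interaction condition attached.

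**The concern.** Readers use subgroup displays mainly to judge whether the effect is consistent. That judgement needs estimates and intervals for all the prespecified factors. Under this rule, a factor's estimates are called for only when its own interaction test gives a small p-value, so the specified output is a sample selected for apparent disagreement between levels.

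Two things follow. The differences shown are exaggerated, because only large observed differences pass. Factors that do not pass, either because the effect really is consistent or because the test had little power, have no specified estimates. A reader could then be unable to check children, nephrotic patients or regions. The rule also works against a sponsor whose effect is homogeneous, since only factors that look discordant would appear. And where a plan is silent, display becomes a choice made after the results are known.

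**Working it through.** **1. Does the condition cover all the efficacy endpoints named for subgroups?** Under SAP sections 8.5 to 8.8, the slopes use mixed-effects models, the percent change from Week 6 to Week 108 and the by-visit eGFR and UP/C changes use repeated-measures models, the Week 112 endpoints use ANCOVA, and the surrogate uses a logit model. All are model-based, so all are covered. Neither document plans a forest plot or an unconditional table of efficacy by subgroup. The planned summary of subgroup characteristics by treatment group describes patients, not treatment effects.

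**2. Number of baseline factors.** Counting the bullets and sub-bullets under "Baseline subgroups of interest are as follows": age, age at diagnosis, sex, race and BMI (5); randomization strata (1); baseline eGFR in two groupings (2); baseline UP/C (1); prior RAAS inhibitor use (5); baseline medication use (6); years since diagnosis, region, cardiovascular history, hypertension history and podocyte mutation (5). The total is 25. Six post-baseline factors make 31.

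**3. Expected passes with no true interaction.** 25 x 0.20 = 5.0 baseline factors per endpoint (31 x 0.20 = 6.2 with the post-baseline factors). This expectation does not need the factors to be independent.

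**4. Selection effect with no true interaction.** For a two-level factor, passing at 0.20 two-sided means |z| > 1.2816. The mean of |z| given passage is φ(1.2816)/0.10 = 1.755. The unselected mean is 2φ(0) = 0.798. The ratio is 1.755/0.798 = 2.2.

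**5. Scale on the eGFR total slope.** SAP section 4.3.1.2 gives SD 5.50, about 150 patients per arm and a projected difference of 2.1 mL/min/1.73 m² per year.
- SE of the treatment difference = 5.50 x √(2/150) = 0.635.
- Check on the plan's own figure: power = Φ(2.1/0.635 − 1.96) = 91.1%, which agrees with the stated 90% or more.
- Interaction SE for a two-level factor with share f = 0.635 x √(1/f + 1/(1−f)), which is 1.27 at f = 0.5.

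The documents give no subgroup shares, so f is an assumption and a range is shown. A slope interaction is also assumed. Probability of display = Φ(d/SE − 1.2816) + Φ(−d/SE − 1.2816), where d is the true between-level difference. The last column is 1.755 x SE.

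| Share f | Interaction SE | Smallest difference shown (1.2816 x SE) | Displayed if d = 1 | Displayed if d = 2 | Mean absolute difference shown if d = 0 |
|---|---|---|---|---|---|
| 0.5 | 1.27 | 1.63 | 33% | 62% | 2.23 |
| 0.3 | 1.39 | 1.78 | 31% | 57% | 2.43 |
| 0.2 | 1.59 | 2.03 | 28% | 50% | 2.79 |
| 0.1 | 2.12 | 2.71 | 25% | 38% | 3.71 |

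At 50:50 with no true interaction, the mean difference shown (2.23) exceeds the whole projected effect of 2.1. The two levels average 3.21 and 0.99 when selected, against 2.61 and 1.59 when every factor is shown and a true 2.1 in both. One level is pushed up and the other down.

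**6. With a true interaction of 2.1 at 50:50.** By simulation, the factor passes 65% of the time. The mean absolute difference is 2.83 when shown and 2.15 unselected, a ratio of 2.83/2.15 = 1.3.

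**The case against.** Several limits are fair, and all of them stand.

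- A reader might infer that all subgroup results are withheld. They are not: adverse-event subgroup summaries carry no such condition.
- A reader might infer that the SAP forbids showing consistent factors. It is silent, not prohibitive. It says without condition that the endpoints are analyzed by subgroup, and the table shells, which are not among these documents, might show more. The supportable statement is that no by-level efficacy output is specified at 0.20 or above. Still, the conditional sentence is the only presentation instruction, and it would be redundant if every level were shown anyway.
- A reader might infer that what is shown is selected purely by chance. That holds only if effects are homogeneous. With real heterogeneity the selection is partly signal, and the exaggeration falls from about 2.2-fold to about 1.3-fold in the case worked above. What is exaggerated is the difference between levels, not the overall treatment effect.
- The 33% and 62% figures do not describe children or regions. Region, race and the randomization strata have four levels each, and the share of children is not given. They also assume an interaction on slope. SAP section 8.3 names only a treatment-by-factor term, whereas the treatment effect in the slope models is carried by treatment-by-time terms. They use the total-slope SD and do not carry over to the proteinuria endpoints.
- Five is an upper-end count. The size rule may remove sparse factors, and many of the rest overlap (two eGFR groupings, UP/C within the strata and again at baseline, individual RAAS classes and any RAAS inhibitor), so five passes are not five separate signals.
- Low power for interactions comes from the trial's size, and showing every factor does not add power. As a screening flag, 0.20 is acceptable.

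None of this removes the problem, which is tying presentation to the flag.

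**Conclusion.** The point holds as a minor reporting weakness, limited to model-based efficacy endpoints. As written, the rule specifies estimates for factors whose levels appear to differ and specifies none for the rest. If effects are homogeneous, about 5 of 25 baseline factors per endpoint are expected to pass (fewer after the size rule), with between-level differences averaging about 2.2 times the unselected size. The inflation factor assumes a two-level factor and a normal test statistic. For a true difference of 2.1 mL/min/1.73 m² per year at 50:50 the inflation is about 1.3-fold. The display probabilities of 33% and 62% are an illustration only, at an assumed 50:50 share with a slope interaction, and they are lower with unequal shares.

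A reader might also infer that the trial's main conclusions are at risk. The documents do not support that: the hierarchy in SAP section 8.4 contains no subgroup test, so no confirmatory alpha or conclusion is affected.

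**What to change.** Replace the last sentence of the rule in SAP section 8.3. For every prespecified baseline subgroup that meets the size rule, present the treatment-effect estimate and 95% confidence interval at each level, for example in a forest plot, with the interaction p-value alongside. Keep 0.20 only as a flag for closer reading, not as the condition for display.

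The cost is a SAP wording change and more tables and figures. No new data are needed, and the design and the testing hierarchy are unchanged.
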